##### 5.3.3.1.2. Analytical Details for Sensitivity Analysis

The model will include the change from Baseline in ALSFRS-R total score at each study visit as the dependent variable and the following list of independent variables as fixed effects: actual time on the study (months), the interaction between time and treatment (0 = placebo, 1 = ravulizumab), age, sex, baseline ALSFRS-R total score, baseline SVC percent predicted,

months since first muscle weakness onset at Baseline, and the stratification factors. The participant-specific random slope will also be added to the model with an unstructured variance-covariance matrix to model the correlations among repeated measurements within each participant. The following covariance structures will be implemented if a convergence issue occurs in the specified order:

- Heterogeneous toeplitz (TOEPH)
- Heterogeneous autoregressive (1) (ARH (1))
- Heterogeneous compound symmetry (CSH)
- Toeplitz structure (TOEP)
- Autoregressive (1) (AR (1))
- Compound symmetry (CS)

The first covariance structure that converges will be used. The Kenward-Rogers method will be used to estimate the denominator degrees of freedom.

No imputation for the missing data will be performed after discontinuation (death or dropout) from the study, assuming the data are missing at random (MAR).

Section 6.2.9 provides details on implementing analysis windows.

A 2-sided p-value less than  $\alpha = 0.05$  associated with the higher mean change in ALSFRS-R total score in the ravulizumab group compared to placebo will indicate a statistically significant treatment benefit. The LS-means and the 95% CIs of the mean change from Baseline at Week 50 for each treatment arm and the difference between the arms will be calculated. The treatment effect will be evaluated via the estimated treatment-by-visit interaction term at Week 50 (Month 11.5). Details will be provided in a listing.

#### 5.3.4. Other Analyses

The ALSFRS-R total score and change from Baseline will be summarized descriptively by visit. Details will be provided in a listing.

Mean score and mean change from Baseline over time, along with 95% CI, will be plotted for ALSFRS-R total score.

**Table 3: Overview of Estimands, Intercurrent Events, and Analyses Related to the Primary Endpoint**

Analysis	Reference Section	ICE	Estimand Strategy
Primary Analysis - CAFS	Section 5.3	Death	Composite strategy
Sensitivity Analysis	Section 5.3.3.1	None	Treatment policy strategy

Abbreviations: CAFS = combined assessment of function and survival; ICE = intercurrent event

## **5.4. Secondary Estimands and/or Endpoints Analysis**

### **5.4.1. Key Secondary Estimands**

#### **5.4.1.1. Time to Ventilation Assistance Free Survival**

##### **5.4.1.1.1. Estimand**

The 5 attributes for the estimand related to VAFS are described as follows:

- Treatment: ravulizumab or placebo with or without the use of stable riluzole and edaravone
- Population: adult participants with ALS as defined by the protocol inclusion/exclusion criteria
- Variable: time (months) from Day 1 (first dose of study drug in RCP) to a VAFS event during the RCP; the VAFS event is defined as the earliest of
  - Death
  - The first use of noninvasive ventilation (NIV) for  $\geq 22$  hours per day for  $\geq 10$  consecutive days
  - The first use of permanent assisted ventilation (PAV) for  $\geq 22$  hours per day for  $\geq 7$  consecutive days VAFS
- ICE: none. the treatment-policy estimand will be used
- Population-level summary: HR (ravulizumab versus placebo)

##### **5.4.1.1.2. Main Analytical Approach**

The treatment effect on the time to VAFS will be analyzed based on a Cox proportional hazards model with treatment as a fixed effect adjusting for age, sex, baseline ALSFRS-R total score, baseline SVC percent predicted, months since first muscle weakness at Baseline, and the stratification factor. A censoring indicator will be equal to 1 if the participant did not experience a VAFS event (considered “censored”), and 0 if the participant experienced an event. Censored participants will include participants who discontinue the study without a VAFS event or complete the RCP without a VAFS event.

The HR of ravulizumab versus placebo will be estimated with its associated 95% CIs. A 2-sided p-value less than  $\alpha = 0.05$  associated with the  $HR < 1$  will indicate a statistically significant treatment benefit.

The components of VAFS will be analyzed separately using similar models to decompose the contribution of each component to VAFS, ie, using the first event of the 3 components. The total number of participants experiencing the first event will be equal to the total number of participants experiencing the VAFS event. Given the composite nature of VAFS, the p-value associated with each component (death, NIV, and PAV) need not be significant.

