#### **9.4.5.4. Multiplicity Adjustment**

If the primary analysis is statistically significant, the study wise Type I error will be controlled using Hochberg method for multiplicity adjustment of the p-values corresponding to the two secondary endpoints (VAFS and change in SVC).

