## 5. STATISTICAL ANALYSES

### 5.1. General Considerations

All data collected in this study will be presented using summary tables, figures, and data listings.

- For the RCP, data summaries and inferential analyses will be presented by the treatment arms (“Ravulizumab” and “Placebo”). For certain noninferential summaries (demographics, baseline characteristics, and other prestudy information, including medical and ALS history, prior medications, and SAEs captured between screening and first infusion), a “Total” group may be formed by combining participants from both treatment arms. No “Total” group will be formed for efficacy and safety-related summaries.
- For the OLE Period, data summaries will be presented by the treatment arms (“Ravulizumab/Ravulizumab” and “Placebo/Ravulizumab”). A “Total” group may be formed by combining participants from both treatment arms.

Statistical analyses will include tabulations of summary data, inferential analyses, by-patient listings, and figures. The summary statistics for continuous variables will include, but not be limited to, the number of participants, mean, SD, minimum, median, and maximum. For categorical variables, frequencies and percentages will be presented. Inference from efficacy analyses will be based on a 2-sided Type I error ( $\alpha$ ) = 5% unless stated otherwise. The 95% confidence intervals (CI) will be produced where applicable. All p-values and CIs will be used for descriptive purposes only due to the study meeting the futility criterion.

Since the study has stopped for futility, multiplicity adjustment will not be considered.

The baseline value for analysis and reporting will be based on the last non-missing measurement on or prior to the first dose of the study drug unless stated otherwise.

Missing safety data will not be imputed.

Analyses will be performed using the SAS® software Version 9.4 or higher. Adverse events (AEs) will be coded with Medical Dictionary for Regulatory Activities (MedDRA) Version 24.0 or later. Prior and concomitant medications will be coded with World Health Organization (WHO) Drug Dictionary Version 202103 or later.

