### 5.3.2. Main Analytical Approach

The analysis of CAFS ranks will be based on an analysis of covariance model. The model will include the CAFS ranks as the dependent variable and the following list of independent variables: treatment indicator (0 = placebo, 1 = ravulizumab), age, sex, baseline ALSFRS-R total score, baseline SVC percent predicted, months since first muscle weakness onset at Baseline, and the stratification factors.

If the 2-sided p-value associated with the higher mean rank in the ravulizumab group compared to the placebo is less than  $\alpha = 0.05$ , a statistically significant treatment benefit will be established. The least squares (LS)-means and the 95% CIs of the CAFS ranks for each treatment arm and the difference between the arms will be calculated. Details will be provided in a listing.

This analysis will be conducted for sake of completion and will not support efficacy conclusion as the study met the pre-specified futility criteria.

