##### **5.4.1.2.2. Main Analytical Approach**

The treatment effect on SVC percent predicted will be evaluated based on a mixed-effect model repeated measure with the change from Baseline in SVC percent predicted as the dependent variable and the following list of independent variables as fixed effects: actual time on study (months), time and treatment interaction, age, sex, baseline ALSFRS-R total score, baseline SVC, disease duration, and the stratification factor. In addition, the participant-specific random slope will be added to the model with an unstructured variance-covariance matrix. The strategy for selecting other covariance structures outlined in Section 5.3.3.1.2 will be used if a convergence issue occurs. The Kenward-Rogers method will be used to estimate the denominator degrees of freedom. No imputation for the missing data will be performed after death or discontinuation, assuming the data are MAR.

A 2-sided p-value less than  $\alpha = 0.05$  associated with the higher mean change in SVC percent predicted in the ravulizumab group compared to placebo will indicate a statistically significant treatment benefit. The LS-means and the 95% CIs of the mean change from Baseline at Week 50

(month 11.5) for each treatment arm and the difference between the arms will be calculated. Details will be provided in a listing.

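### SAP version 2 makes every p-value descriptive, yet four of its analysis sections still turn p < 0.05 into a significant-benefit finding, and the VAFS and SVC rules omit the protocol's gate

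*SAP*

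**What the plan says.** SAP section 5.1 sets the general rule after the futility stop: "All p-values and CIs will be used for descriptive purposes only due to the study meeting the futility criterion". It also says: "Since the study has stopped for futility, multiplicity adjustment will not be considered". The same section still contains a sentence of the confirmatory kind: "Inference from efficacy analyses will be based on a 2-sided Type I error" of 5%, unless stated otherwise.

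The analysis sections then give endpoint-specific rules, each at a two-sided 0.05 with the effect favouring ravulizumab:

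- **5.3.2, CAFS ranks:** "a statistically significant treatment benefit will be established". The section closes by saying that the analysis is done for completeness and does not support an efficacy conclusion.
- **5.3.3.1.2, ALSFRS-R sensitivity model:** a p-value below 0.05 "associated with the higher mean change in ALSFRS-R total score in the ravulizumab group compared to placebo will indicate a statistically significant treatment benefit".
- **5.4.1.1.2, VAFS:** a p-value below 0.05 with a hazard ratio under 1 "will indicate a statistically significant treatment benefit".
- **5.4.1.2.2, SVC percent predicted:** a p-value below 0.05 "associated with the higher mean change in SVC percent predicted in the ravulizumab group compared to placebo will indicate a statistically significant treatment benefit".

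Protocol 9.4.5.4 treats VAFS and SVC differently: "If the primary analysis is statistically significant, the study wise Type I error will be controlled using Hochberg method for multiplicity adjustment" of those two endpoints.

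**The concern.** A descriptive p-value cannot establish a benefit, so the SAP gives two incompatible readings of the same result. Three things keep the general rule in 5.1 from settling the matter cleanly.

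First, the authors put a local limit on CAFS but not on the other three analyses, so a reader may take the difference as deliberate. Second, 5.1 is itself mixed, since it still speaks of inference at a 5% error rate. Third, 5.4.1.1.2 remarks that the individual VAFS components do not have to reach significance because VAFS is a composite. That remark treats significance of the composite as something that still counts.

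At stake is what the report may say. VAFS is a survival composite in ALS. A report author could quote 5.4.1.1.2 exactly to present a nominal p < 0.05 as a significant benefit in a trial that stopped for futility, with neither the gate nor the Hochberg step behind it.

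**Working it through.** **1. The passages side by side**

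| SAP section | Analysis | 0.05 benefit rule | Local limit on conclusions | Primary gate or Hochberg |
|---|---|---|---|---|
| 5.3.2 | CAFS ranks | yes | yes | not applicable (primary) |
| 5.3.3.1.2 | ALSFRS-R model | yes | none | none (sensitivity analysis) |
| 5.4.1.1.2 | VAFS | yes | none | none |
| 5.4.1.2.2 | SVC | yes | none | none |

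The protocol's own methods for the ALSFRS-R sensitivity model (9.4.5.1.2.1) and for VAFS and SVC (9.4.5.2) contain no such 0.05 rule. In the documents available, those three rules appear only in the SAP.

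**2. Inputs**

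- Two-sided alpha of 0.05 (SAP 5.1). Each rule also requires the favourable direction, so under no effect each fires with probability 0.05 / 2 = 0.025.
- Protocol procedure: primary at 0.05, then Hochberg over VAFS and SVC (protocol 9.4.5.4).
- Correlations between test statistics: not given in the documents. Assumed 0 to 0.5 between endpoints.
- Method for the correlated cases: 1,000,000 multivariate normal draws per scenario, no effect on any endpoint.

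**3. The plan's own figure**

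The SAP gives no study-wise error rate once the adjustment is dropped. For the protocol's gated procedure, the simulated study-wise error in either direction is 4.99% to 5.03%, which agrees with the intended 5%.

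**4. VAFS and SVC under the local rules, no gate**

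- Benefit direction, independent: 1 − (1 − 0.025)² = 0.0494, or 4.9%.
- Benefit direction, simulated: 4.7% at correlation 0.3 and 4.5% at 0.5.
- Either direction, independent: 1 − (1 − 0.05)² = 0.0975, or 9.8%. Simulated: 9.5% at 0.3 and 9.0% at 0.5.

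**5. VAFS and SVC under the protocol's gate and Hochberg, either direction**

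- Under independence, Hochberg rejects at least one of the two with probability 0.05² + 2 × 0.025 × 0.95 = 0.0025 + 0.0475 = 0.05.
- Multiplied by the gate: 0.05 × 0.05 = 0.0025, or 0.25%.
- Simulated: 0.5% at correlation 0.3 and 1.0% at 0.5.

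**6. Comparison**

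Like for like in either direction, 9.0% to 9.8% ungated stands against 0.25% to 1.0% gated. In the benefit direction the ungated figure is 4.5% to 4.9%. The gated figure for benefit claims cannot exceed its either-direction value, so about 1% is an upper figure for it.

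**The case against.** The strongest reply is that the controlling rule is already present. Section 5.1 covers all p-values and confidence intervals, which includes VAFS and SVC, and Appendix 4 says that the sentence was added to explain how they are to be interpreted. This stands. A reader might infer that, as written, p < 0.05 for VAFS or SVC is a declared benefit. Read with 5.1 it is not: the p-value is descriptive, and error inflation arises only if the local sentence is followed over the general one.

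A reader might also count all four rules and quote 1 − 0.975⁴ = 9.6%. That arithmetic is right, but the figure does not fit the point. CAFS is expressly barred from supporting an efficacy conclusion. The ALSFRS-R model is a sensitivity analysis of the same endpoint, so it lies outside the protocol's multiplicity scheme and is not independent of CAFS. With assumed correlations of 0.8 to 0.9 between those two and 0 to 0.5 elsewhere, the four-rule figure falls to 7.1% to 8.7%. The gate matters for VAFS and SVC, so the figure for those two is the relevant one.

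A further reply is that dropping formal multiplicity control after a futility stop, with p-values declared descriptive, is acceptable. That also stands, and nothing here asks for Hochberg to be restored. What the reply does not remove is the wording conflict: one section has a local limit, three have none, and 5.1 keeps its 5% inference sentence.

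**Conclusion.** The conflict is real and worth correcting, because the four sentences are live decision rules that report authors follow. Its proper description is residual significance wording at odds with a descriptive-only rule, not a plan that has lost error control.

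The size is conditional. If the local VAFS and SVC rules were followed instead of 5.1, a false benefit declaration on at least one of them would have a 4.5% to 4.9% chance, against about 1% or less under the protocol's gated procedure. This assumes no effect on any endpoint and between-endpoint correlations of 0 to 0.5, which are assumptions. The figures are also unconditional: they take no account of the trial having met a futility criterion assessed on ALSFRS-R data, and the documents do not allow that to be quantified. The gate used is the CAFS primary analysis; the protocol's alternate primary analysis for the EMA submission is not part of the comparison.

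A reader might infer that version 2 stripped Hochberg out of SAP version 1 and left that version's rules in place. Version 1 is not among the documents, so this cannot be shown. What can be shown is that version 2 departs from protocol 9.4.5.4.

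**What to change.** 1. Delete the significance sentence in each of 5.3.2, 5.3.3.1.2, 5.4.1.1.2 and 5.4.1.2.2. Alternatively, replace each with one statement: *estimates, 95% CIs and nominal p-values are reported descriptively, without a claim of statistical significance (Section 5.1)*.
2. Align the 5% Type I error sentence in 5.1 with the descriptive-only rule, for example by saying that 0.05 only sets the confidence level of the reported intervals.
3. Log in Appendix 4 that the protocol's primary gate and Hochberg step no longer apply, and why. The appendix is titled as a list of changes to protocol-planned analyses; it records the descriptive-only sentence but not this change.

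No added statement that a VAFS or SVC benefit is not claimed is needed. It would fix a conclusion before the final data are seen, and the steps above already resolve the conflict.

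The cost is an edit to the SAP text. No model, estimate, interval, dataset or program changes.

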##### **5.4.1.1.3. Other Analyses Related to VAFS and Components of VAFS (NIV, PAV and Mortality)**

An analysis for time (months) to NIV, PAV, and death will be performed separately with a Cox proportional hazards model similarly to that described in Section 5.4.1.1.2. However, these

analyses are different from the analyses of the VAFS components; for example, a participant may experience an event of NIV followed by death; hence, NIV will contribute to VAFS, but death will not. Hence the total number of participants experiencing any of these events may be greater than the total number of participants experiencing the VAFS event.

For VAFS and its components, the Kaplan-Meier curves by treatment group will be produced. Estimated survival probabilities at Week 50 (Month 11.5) will be provided for both treatment groups. The number and percentage of participants experiencing a VAFS event and its components will be provided. In addition, the number and percentage of deaths will be summarized by the associated reasons.

The number and percentage of participants with ventilator use (regardless of the number of hours) at least once during RCP, NIV, and PAV will be summarized. Details will be provided in listings.

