### 3. SAMPLE SIZE DETERMINATION

The sample size calculations were based on information extracted from the PRO-ACT (Pooled Resource Open-Access ALS Clinical Trials) database consisting of clinical trials data pooled from 23 Phase 2/3 ALS clinical trials. Approximately 354 patients will be randomized to ravulizumab or placebo in a 2:1 ratio.

The mean change in ALSFRS-R total score in the placebo arm at Week 50 is estimated as -14.3 (assuming a monthly linear slope of the decline of 1.19 calculated based on the proposed study inclusion criteria). Assuming a 30% relative reduction in the monthly slope in the ravulizumab group is considered a clinically meaningful treatment effect (Castrillo-Viguera, 2010; Writing Group for Edaravone ALS Study., 2017), the mean change in ALSFRS-R total score at Week 50 is estimated as -10. A common standard deviation (SD) of 10.3 was estimated for the change from Baseline in ALSFRS-R total score. A total of 282 patients will be required to ensure at least 90% nominal power based on a 2-sided t-test (Type I error = 0.05) for detecting a non-zero treatment effect for ALSFRS-R (defined as the difference between ravulizumab and placebo in the mean change from Baseline in ALSFRS-R total score at Week 50). The total sample size is estimated as 354 after adjusting for a 20% dropout (Cudkowicz, 2013). Furthermore, assuming approximately 82% 1-year survival rate for placebo group and 50% relative reduction in the HR for mortality due to treatment with ravulizumab, this sample size will provide at least 90% nominal power based on the primary analysis (CAFS).

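### Kaplan-Meier Week 50 probabilities for NIV and PAV leave death before ventilation unhandled and so slightly overstate the chance of reaching ventilation; cumulative incidence should be reported instead

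*SAP*

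**What the plan says.** SAP 5.4.1.1.3 covers VAFS and its parts: death, NIV and PAV. It plans three kinds of output that matter here.

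- Separate models: "An analysis for time (months) to NIV, PAV, and death will be performed separately with a Cox proportional hazards model similarly to that described" for VAFS in 5.4.1.1.2.
- Curves and point estimates: "For VAFS and its components, the Kaplan-Meier curves by treatment group will be produced", followed directly by "Estimated survival probabilities at Week 50 (Month 11.5) will be provided for both treatment groups".
- Crude counts: "The number and percentage of participants experiencing a VAFS event and its components will be provided".

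The only censoring rule is written for the composite, in 5.4.1.1.2: "Censored participants will include participants who discontinue the study without a VAFS event or complete the RCP without a VAFS event". The estimand in 5.4.1.1.1 reads "ICE: none. the treatment-policy estimand will be used". That is coherent for VAFS, where death is itself an event, but it gives no strategy for death when NIV or PAV is analysed alone. Neither the SAP nor the protocol mentions cumulative incidence, Aalen-Johansen, Fine-Gray or any other competing-risk method.

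**The concern.** A patient who dies before starting qualifying ventilation can never have that event. In a Kaplan-Meier analysis of time to NIV or PAV there is nowhere to put that patient except among the censored. The estimator removes the patient from the risk set at death and assumes that the later ventilation risk would have matched that of patients still under observation. After a death the later risk is zero. One minus Kaplan-Meier therefore estimates ventilation risk in a setting where nobody dies first, not the proportion of patients who reach ventilation by Week 50, and it is at least as large as that proportion.

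The plan expects different mortality in the two arms, so the size of the excess would generally differ between them. A reader who takes the Week 50 figures as the chance of needing ventilation would get a number that is too high, by different amounts in each arm.

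**Working it through.** **Inputs from the documents.** SAP section 3 gives the mortality assumption, "assuming approximately 82% 1-year survival rate for placebo group and 50% relative reduction in the HR for mortality due to treatment with ravulizumab", read here as a hazard ratio of 0.5. It also gives the allocation, "Approximately 354 patients will be randomized to ravulizumab or placebo in a 2:1 ratio", that is 118 placebo and 236 ravulizumab. Week 50 is Month 11.5 (SAP 5.4.1.1.3), so T = 11.5/12 = 0.958 years.

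**Assumptions.** The documents state no NIV or PAV rate and no Week 50 ventilation probability, so the plan has no figure of its own to reproduce on this point. I assume constant hazards and the same ventilation hazard h in both arms, and show a range of rates.

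**Step 1, deaths by Week 50.**
- Placebo: d = -ln(0.82) = 0.198 per year; 1 - exp(-dT) = 17.3%, about 20 of 118.
- Ravulizumab: d = 0.099 per year; 1 - exp(-dT) = 9.1%, about 21 of 236.

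**Step 2, the two estimators.**
- Kaplan-Meier with deaths censored: 1-KM = 1 - exp(-hT), the same in both arms when h is equal.
- Cumulative incidence with death competing: h/(h+d) × [1 - exp(-(h+d)T)].

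Example at 1-KM = 10%: h = -ln(0.90)/0.958 = 0.110. Placebo: 0.110/0.308 × [1 - exp(-0.2955)] = 0.3565 × 0.2559 = 9.12%. Ravulizumab: 0.110/0.209 × [1 - exp(-0.2005)] = 0.5256 × 0.1816 = 9.55%.

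| 1-KM, both arms | Incidence, placebo | Incidence, ravulizumab | Excess, placebo (points; relative) | Excess, ravulizumab (points; relative) |
|---|---|---|---|---|
| 2% | 1.82% | 1.91% | 0.18; 9.8% | 0.09; 4.8% |
| 5% | 4.56% | 4.77% | 0.44; 9.7% | 0.23; 4.8% |
| 10% | 9.12% | 9.55% | 0.88; 9.6% | 0.45; 4.7% |
| 20% | 18.28% | 19.11% | 1.72; 9.4% | 0.89; 4.6% |
| 30% | 27.47% | 28.70% | 2.53; 9.2% | 1.30; 4.5% |

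With equal hazards Kaplan-Meier shows no arm difference. The incidence is 0.1 to 1.2 points higher on ravulizumab, because fewer of its patients die first.

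**Step 3, simulation.** I used 4000 trials of 118 and 236 patients with 20% dropout at each of three rates. At 10%, mean 1-KM and Aalen-Johansen were 10.1% and 9.2% on placebo, and 10.1% and 9.6% on ravulizumab. The standard error of the placebo 1-KM was 3.1 points (2.3 at a 5% rate, 4.1 at 20%). The Aalen-Johansen estimate never exceeded 1-KM in the placebo arm, where this was checked.

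**Step 4, unequal ventilation hazards.** With 1-KM of 5% on placebo and 10% on ravulizumab, the excess is 0.44 and 0.45 points. At 5% and 15% it is 0.44 and 0.67, so the order reverses. The relative excess stays at about 9.7% and 4.7%.

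**Step 5, the first-event reading.** SAP 5.4.1.1.2 also defines component analyses by which event came first. On that reading death competes too. For placebo at the 10% rate, taking death and one ventilation event only, separate Kaplan-Meier estimates add to 17.3% + 10.0% = 27.3%, while the probability of either event is 1 - exp(-0.2955) = 25.6%. Cumulative incidences (9.1% and 16.5%) add to 25.6%.

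**The case against.** The SAP never writes that deaths are censored in the NIV and PAV analyses. The written rule concerns VAFS, and 5.4.1.1.3 is silent on death before ventilation. A reader might infer that the plan specifies this censoring; it does not. The censoring is a consequence of applying Kaplan-Meier to a non-fatal event with no other rule given. The sentence on Week 50 probabilities also does not say whether it covers the components or only VAFS, although it directly follows the one that names both. These limits stand. They change the point from a wrong rule to an unstated one, and either way the text needs completing.

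Kaplan-Meier with deaths censored and cumulative incidence are different target quantities, and the SAP does not say which is intended. With equal hazards, an absence of arm difference on Kaplan-Meier is a correct statement about hazards. That is fair, but the Cox models already address hazards. A Week 50 probability is naturally read as the share of patients who reach the event.

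The crude counts and percentages are also reported, with deaths by reason and listings, so a reader can see much of what happened. They do not replace the estimate: crude percentages ignore incomplete follow-up, which matters with 20% dropout planned and a study stopped for futility.

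Finally, little depends on this. The qualifying definitions are strict (at least 22 hours a day for 10 or 7 consecutive days), so low rates are possible. At 10% the placebo excess is 0.0088 × 118, about one patient. SAP 5.1 makes all p-values and confidence intervals descriptive. This stands, and it sets the priority.

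**Conclusion.** The gap is real and minor. As written, the plan would give Week 50 Kaplan-Meier figures for NIV and PAV that overstate the probability of reaching ventilation. The direction follows from the method. The size rests on the planning mortality, which is an assumption and not an observed result, on constant and equal ventilation hazards, and on a range of rates that the documents do not supply. Over 2% to 30% the excess is about 0.2 to 2.5 points on placebo and 0.1 to 1.3 on ravulizumab, well inside sampling error at the rates simulated.

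Three stronger conclusions are not supported. First, the excess is not always larger in the arm with more deaths: in absolute points this needs similar ventilation hazards, and Step 4 shows it vanishing and reversing. Second, the VAFS result and the all-cause death curve are unaffected, because death is an event in both. Third, the Cox models for NIV and PAV are not invalid; they can be read as cause-specific hazards.

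**What to change.** In SAP 5.4.1.1.3:

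- For NIV and for PAV, report Aalen-Johansen cumulative incidence by arm at Week 50, with death before the event as a competing event and loss to follow-up as censoring.
- Keep Kaplan-Meier for VAFS and for all-cause death.
- Keep the Cox models and label those for NIV and PAV as cause-specific, with follow-up ending at death.
- Say which meaning of components the curves use. If it is the first-event decomposition of 5.4.1.1.2, report cumulative incidence for all three first-event types (death, NIV, PAV), each competing with the other two. These then add up to the VAFS event probability, in line with the SAP's own statement that the first-event counts total the VAFS events.

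The cost is a few sentences of SAP text and a different estimation option in the same analysis. No new data, visits or design changes are needed.
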